6.3.2 Summary Statistics

In general, data will be summarized by means of summary statistics. Continuous data will be presented with the number of observations, mean value, standard deviation, minimum, Q1, median, Q3 and maximum value. Categorical data will be presented as counts and percentages. All efficacy related variables will be summarized for the FAS population and all safety related data will be summarized for the safety population.

For any assessments being evaluated by visit, an LOCF (Last observation carry forward) approach will be applied, where the last available information will be combined, independently of what the last recorded visit is.

All descriptive statistics will be presented by stratum of high- and intermediate risk patients and pooled together and by treatment group.

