7 INVESTIGATIONAL PLAN

7.1 Study Design and Plan-Description

The study is an open-label, randomized, controlled, two (2) armed, multicenter, phase II study. Intermediate- and high-risk mRCC patients according to Heng criteria are eligible for participation [4]. Stratified randomization based on Heng-risk categories applies. The patients are randomized in a consecutive order to one (1) of the following two (2) treatment arms when eligibility has been confirmed;

- (i) Two (2) doses of Intuvax (10×10^6 DCs) administered intratumorally into the primary tumor 14 ± 3 days apart followed by nephrectomy at least three (3) days after the second vaccine dose.

AND

Sunitinib treatment initiated five (5) to eight (8) weeks after nephrectomy, administered dose in accordance with the SmPC/USPI.

- (ii) Sunitinib treatment initiated five (5) to eight (8) weeks after nephrectomy, administered dose in accordance with the SmPC/USPI.

The estimated number of patients to be randomized in the study is around 90. The patients will be randomized in a 2:1 (vaccine treatment arm [i]:control treatment arm [ii]) ratio. Stratification will be done at randomization for intermediate- and high-risk patients.

Patients randomized to treatment arm (i) are scheduled for 12 study visits and patients randomized to treatment arm (ii) are scheduled for 10 study visits during a study period of 78 weeks, see list below and *Figure 1*. In addition, all patients being exposed to any of the Investigational Medicinal Products (IMPs) will have a safety evaluation done for collection of SAEs up to 30 days after last dose of IMP administered in the study. The following visits apply for the two (2) patient populations:

- Screening Visit (Screening)
- Vaccination 1 Visit (Vacc1), applicable for patients randomized to treatment arm (i)
- Vaccination 2 Visit (Vacc2), applicable for patients randomized to treatment arm (i)
- Nephrectomy Visit (Nephrectomy)
- Sunitinib Start Visit (Sun-Start), five (5) to eight (8) weeks after Nephrectomy
- Sunitinib Follow-up Visits (SFU[6W] and SFU[12W]), every 6 weeks for 12 weeks or until locally CT-verified PD whichever occurs first
- Sunitinib Follow-up Visits (SFU[24W], SFU[36W], SFU[48W], and SFU[60W]), every 12 weeks until End-of study or until locally CT-verified PD whichever occurs first
- End-of-Study Visit (End-of-Study)

[figure not shown]

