7.2.1.6 SFU[6W], SFU[12W], SFU[24W], SFU[36W], SFU[48W], and SFU[60W]

These visits are applicable for all patients unless locally CT-verified PD occurs. In case of PD this visit should be considered the End-of-Study Visit.

If SFU[60W] is scheduled ≥ 76 weeks since Screening this visit should be considered the End-of-Study Visit, *Section 7.2.1.7*.

TIME WINDOWS:

SFU[6W]: 6 weeks (± 7 days) after Sun-Start Visit
SFU[12W]: 12 weeks (± 7 days) after Sun-Start Visit
SFU[24W]: 24 weeks (± 7 days) after Sun-Start Visit
SFU[36W]: 36 weeks (± 7 days) after Sun-Start Visit
SFU[48W]: 48 weeks (± 7 days) after Sun-Start Visit
SFU[60W]: 60 weeks (± 7 days) after Sun-Start Visit

NB: The CT/MRI scans do not have to be done the very same day as the corresponding study visits. However, each CT/MRI scan has to be done within the specified time window for the corresponding visit.

ACTIVITIES AND ASSESSMENTS:

The same activities and assessments will be done at these visits as was done on Sun-Start Visit except for auto- and alloimmunization, *Section 7.2.1.5*. In addition to dispense of sunitinib, the site personnel will collect unused and empty sunitinib packages (distributed at the previous visit) from the patient for drug accountability, *Section 9.1.4*.

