7.2.1.7 End of Study Visit

This visit is applicable for all patients.

TIME WINDOW:

78 ± 2 weeks after Screening

NB: The CT/MRI scan does not have to be done the very same day as the study visit. However, it has to be done within the above specified time window.

ACTIVITIES AND ASSESSMENTS:

The same activities and assessments will be done at this visit as was done on SFU[6W] to SFU[60W] Visits, *Section 7.2.1.6*. No dispense of sunitinib will be done.

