12.1.4 Summary Statistics

In general, data will be summarized by means of summary statistics. Continuous data will be presented with the number of observations, mean value, standard deviation, minimum, Q1, median, Q3 and maximum value. Categorical data will be presented as counts and percentages. Visit related data will be summarized up until and including the Nephrectomy Visit. Following this visit, visit related data may in addition be summarized, if applicable, based on results being re-allocated defined based on time intervals or as last available observation. Details for this will be specified in the SAP.

All individual patient data will be listed.

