6.6 Handling of Dropouts and Missing Data

Primary and secondary efficacy endpoint

The primary and secondary efficacy endpoint analysis will be conducted on available data (observed cases). Missing data due to loss of follow-up and rules for censoring will be done as described in each corresponding section.

Handling of incomplete dates

Incomplete (partial or missing) dates will be presented in data listings as provided on the eCRF. However, for use in calculations (e.g. to calculate the duration of an AE or medication use) dates will be estimated as follows.

For partial start-dates

- If the year is unknown, then the date will not be imputed and will be assigned a missing value
- If the month is unknown, then:
 - If the year matches the year of the first dose date, then impute the month and day of the first dose date
 - Otherwise, assign 'January'
- If the day is unknown, then:
 - If the month and year match the month and year of the first dose date, then impute the day of the first dose date.
 - Otherwise, assign 'January'.

For partial end-dates,

- If the year is unknown, then the date will not be imputed and will be assigned a missing value.
- If the month is unknown, then assign 'December'.
- If the day is unknown, then assign the last day of the month

If the above rules for end-dates result in a date after the patient was ended the study, then the end date will be replaced with the patient's date of completion/withdrawal. Furthermore, should the above rules not result in the most conservative date (as described below), then the imputed value may be replaced by a date that will lead to a more conservative analysis.

After implementing the rules above, to determine whether AEs with incomplete start or stop dates are pre-treatment or treatment-emergent the following strategy will be used:

- If the start date and stop date are both missing, the most conservative approach is taken and the AE is considered to be treatment-emergent
- If the start date is missing but the stop date is not missing and is on or after the day of first study drug administration but before or on the Week 12 visit date then the most conservative approach is taken and the AE is considered to be treatment-emergent;
- If the start date is missing but the stop date is not missing and is before the day of first study drug administration then the AE is considered to be pre-treatment.

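### SAP 6.3.2 applies LOCF to every by-visit assessment with no stop at exit or death; read literally, it distorts the late descriptive tables, so the sentence should be reworded

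*SAP*

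**What the plan says.** The rule is in SAP 6.3.2 (Summary Statistics): "For any assessments being evaluated by visit, an LOCF (Last observation carry forward) approach will be applied". The sentence goes on: "where the last available information will be combined, independently of what the last recorded visit is". No variable is exempted, and neither study exit nor death is named as a stopping point.

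The protocol text behind it is section 12.1.4. It permits, as an optional addition after the Nephrectomy Visit, a summary "based on results being re-allocated defined based on time intervals or as last available observation".

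Follow-up visits end at progression. Protocol 7.1 schedules the later ones "every 12 weeks until End-of study or until locally CT-verified PD whichever occurs first", and protocol 7.2.1.6 adds: "In case of PD this visit should be considered the End-of-Study Visit". The exit visit is a full one (protocol 7.2.1.7): "The same activities and assessments will be done at this visit as was done on SFU[6W] to SFU[60W] Visits".

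Three other SAP rules bear on the same tables:

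- SAP 6.3.11 summarises vital signs and laboratory data as the values observed at each visit, with changes from baseline to the visits at which the parameter was assessed.
- SAP 6.6, on unscheduled visits, places end-of-trial data from early withdrawals at the visit nearest to withdrawal.
- SAP 6.6 opens with a rule limited to efficacy endpoints ("The primary and secondary efficacy endpoint analysis will be conducted on available data (observed cases").

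**The concern.** Because visits stop at progression, a missing late visit is usually missing because of the outcome. LOCF is a named method, and a programmer who follows the first half of the sentence would fill every later planned visit with the patient's last value. Patients who had died would keep a value too.

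The exposed outputs are descriptive: laboratory, vital-sign and physical-examination summaries (SAP 6.3.11), ECOG by visit (Table 14.2.23) and RECIST category by visit (Tables 14.2.13 and 14.2.14). In the counts of abnormal and clinically significant findings and in the shift tables, one measurement could be counted at several visits. The late columns would mix values measured in patients still followed with values frozen at exit.

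The RECIST table after sunitinib start has a specific weakness. Exit follows progression on the local CT reading, while protocol 10.4.3 bases endpoint evaluation on the central reading. SAP 6.3.6 also expects some patients to be discontinued for clinical progression without RECIST PD. If the table uses central readings, such a patient could appear as SD or PR at visits after leaving with progression.

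**Working it through.** The plan gives no figure for this point, so there is none to reproduce. The check compares the texts and then sizes the effect under one reading.

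**Step 1: two readings of SAP 6.3.2.**

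- Fill-forward: the first half of the sentence names LOCF for any by-visit assessment. Each missing later visit takes the last recorded value.
- Single summary: the second half describes combining each patient's last information, whichever visit it came from. With protocol 12.1.4, this fits one additional last-observation summary. No later visit is filled.

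The SAP does not say which is meant.

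**Step 2: the fill-forward reading against the other rules.**

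- SAP 6.3.11 reports observed values at each visit. A carried value is not an observed one, so this is a direct conflict for vital signs and laboratory data.
- SAP 6.6 assigns exit data to one visit, the nearest. Fill-forward would also place them at all later visits.
- Protocol 12.1.4 offers the last-available summary as an optional addition. Fill-forward makes it a blanket rule.
- The observed-case sentence in SAP 6.6 covers primary and secondary efficacy endpoints. Its clear overlap with by-visit tables is limited to Tables 14.2.13 and 14.2.14.

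**Step 3: which analyses could change.** OS and 18-month survival use Kaplan-Meier estimates with censoring (SAP 6.3.5). PFS and TTP are time-to-event analyses with their own censoring rules, and ORR and DCR use best overall response (SAP 6.3.6). None is a by-visit analysis, so none changes under either reading.

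**Step 4: size under the fill-forward reading only.**

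Inputs:

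- SFU[60W] is 60 weeks after Sun-Start (protocol 7.2.1.6): 60 × 7 / 30.44 = 13.8 months.
- Median time from Sun-Start to exit, m: 6 to 11 months. This is an assumption; the documents give no exit rate or PFS figure.
- Exit times are assumed exponential.

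Share still on schedule at time t is 2^(−t/m); the share carried forward is 1 minus that.

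- m = 6: 2^(−13.8/6) = 0.20, so 80% carried.
- m = 11: 2^(−13.8/11) = 0.42, so 58% carried.

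With around 90 patients randomized 2:1 (60 and 30), and if all start sunitinib:

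- Vaccine arm: 0.58 × 60 ≈ 35 to 0.80 × 60 = 48 carried entries.
- Control arm: 0.58 × 30 ≈ 17 to 0.80 × 30 = 24 carried entries.

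Varying the assumed median, by the same formula in weeks:

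| Assumed median (weeks) | Carried at SFU[24W] | Carried at SFU[60W] |
|---|---|---|
| 26 | 47% | 80% |
| 39 | 35% | 66% |
| 52 | 27% | 55% |

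Under the single-summary reading, every one of these shares is zero.

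**The case against.** The best reply is that the sentence, read whole, describes a single last-observation summary. Its second clause says so fairly plainly, and protocol 12.1.4 supports it. The more specific safety text in SAP 6.3.11 would then govern the by-visit tables, and Table 14.1.3 (number of patients by visit) would make attrition visible. This largely stands as an argument about what was intended. It does not remove the ambiguity, because the first clause prescribes a named method for every by-visit assessment.

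A reader might also infer more than the documents support:

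- That SAP 6.3.2 broadly contradicts the observed-case rule in SAP 6.6. It does not: laboratory, vital-sign and physical-examination tables fall outside that rule, and the overlap is two descriptive RECIST tables.
- That late tables would show a falsely stable cohort built from values recorded before exit. The PD visit carries a full set of assessments, so the carried value would usually be the one measured at progression, and the carried RECIST category would normally be PD. The SD or PR case needs local or clinical progression without central RECIST PD.
- That the arms would be distorted differently. This requires different exit times by arm, for which the documents give no figures.
- That efficacy conclusions are at risk. Step 3 of the working shows that they are not.

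**Conclusion.** The point holds as a drafting ambiguity with a potentially large effect on descriptive tables. Taken literally, SAP 6.3.2 would fill late visits with values frozen at exit, including for patients who have died, and would conflict with SAP 6.3.11 and with the nearest-visit rule in SAP 6.6. Taken as one pooled summary, it carries nothing into later visits.

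The 58% to 80% at SFU[60W] applies only to the literal reading and rests on assumed exponential exit with a median of 6 to 11 months. No planned OS, 18-month survival, PFS, TTP, ORR or DCR result changes. The trial is declared exploratory and the affected tables are descriptive, so severity is low. The reason to act is that the two readings give very different late-visit tables and the text does not choose between them.

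**What to change.** Replace the LOCF sentence in SAP 6.3.2 with wording such as: *By-visit tables use observed data with n at each visit; no value is carried past exit or death; a separately labelled last-available-observation row is shown for named variables.* List those variables, and align 6.3.2 with 6.3.11 and with the early-withdrawal rule in 6.6. The extra row keeps the option that protocol 12.1.4 allows.

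This is a free improvement. It needs no new data and no change to any efficacy analysis, and it requires less programming than fill-forward. SAP 6.2 already provides the route: the final SAP or, for a minor clarification after that, the Pre-Analysis Review Form signed before database lock.

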6.3.3 Patient Data Listings

Data collected in the CRF will generally be listed in Appendix 16.2 (see section 0). CRF check questions [e.g. Lab samples taken (Yes/No)] and reminders will not always be listed.

Listings will be sorted by treatment group, study centre and patient number, or by patient number and treatment group.

In CRF modules where a date is recorded, the date and the relative day may be included in the corresponding listing. In modules where both a start date and stop date are recorded, the duration may be included in the listing.

6.3.4 Demographic and Other Baseline Characteristics

Patient disposition and discontinuation, Demographics (Age, Sex and Race) and other baseline characteristics (Weight and Height) and Medical History (mRCC): Duration of mRCC, Primary Tumor Stage, mRCC Symptoms and Severity Grade, Karnofsky Performance Status and other Medical history will be presented using summary statistics by treatment group and by intermediate/high risk stratum. The patient disposition and discontinuation will be based on all screened patients, while the other will be summarised for the Safety population.

6.3.5 Primary Efficacy analysis

This is a descriptive proof of concept study and the sample size is not determined based on a statistical power calculation. Even though the trial is descriptive, some exploratory statistical testing will be conducted for primary endpoint, as described below.

Overall Survival

The primary endpoint is median OS, where OS is defined as the time from randomization to the time of death from any cause.

Median OS after randomization in high-risk and intermediate-risk mRCC patients will be calculated and compared overall and by subgroup based on FAS in the following way:

After the last patient has completed the trial, a collection of survival status, for patients still alive when exiting the study will be conducted by [REDACTED] Drug Safety. Additional collections will be conducted up to 5 years after collection of the last patient's 18 months survival data. For patients who die before end of trial, or patients with a known date of death during the additional collection, the survival time will be calculated as the difference in date of death and randomization date plus 1 day. Patients still alive at last contact, either during the trial or at the additional collection, will be censored at last date patient is known alive. Patients that are lost to follow-up during trial, or alive at end of trial where no follow-up information is available will be censored at last date patient is known alive.

Survival functions will be displayed graphically using Kaplan-Meier plots, and life table statistics will be produced including summaries of number of events and censored observations. Estimates of 25%, 50% (median) and 75% percentiles of time of survival with corresponding 95% confidence intervals will be calculated. Additionally, analyses where the survival functions will be compared between Intuvax+sunitinib, vs. sunitinib alone will be conducted using a stratified log-rank test, controlling for strata (high/intermediate-risk patients).

The analyses will be done overall, and separately for high/intermediate risk group of patients.

In addition, the primary efficacy endpoint will be evaluated using the PPS.

The analyses will be conducted using Proc Lifetest, SAS®.

18-month survival rate

18-month survival rate is defined as the proportion of patients alive 18 months after randomization, or probability of surviving beyond 18 months after randomization.

The 18-month survival rates will be obtained using the same analyses as applied for OS, described above, where the fixed time point estimate, 18-months survival, will be estimated using the Kaplan-Meier estimates as obtained above. The Timelist option in Proc Lifetest will be applied to get the estimated proportions at 18 months. Treatment groups will be compared using a z-test based on the proportions, where the Greenwood formula will be used for calculation of related standard errors. The analysis will be done overall, and separately for high/intermediate risk group of patients. Results will be presented including the estimated proportions with corresponding 95% CIs and the p-value for treatment difference. As the log-rank test for comparison between treatment groups is assessed on the full survival functions, as applied above, while the 18 months survival only utilize a subset of the complete survival data, the results from the treatment comparison based on the latter should be considered with caution.

The endpoint will be evaluated for FAS as the main analysis, although will also be repeated for the PPS population.

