
OVERALL STUDY DESIGN:
 
The study is an open-label, randomized, controlled, two (2) armed, multicenter, phase II study. Intermediate- and high-risk mRCC patients according to Heng criteria are eligible for participation. Stratified randomization based on Heng-risk categories applies.
 
The patients are randomized in a consecutive manner into one (1) of the following two (2) treatment arms;
 
(i) Two (2) doses of Intuvax (10×10^6 DCs) administered intratumorally into the primary tumor 14 \pm 3 days apart followed by nephrectomy at least three (3) days after the second vaccine dose. AND Sunitinib treatment initiated five (5) to eight (8) weeks after nephrectomy. Administered dose in accordance with the Summary of Product Characteristics (SmPC)/United States Product Insert (USPI)
 
(ii) Sunitinib treatment initiated five (5) to eight (8) weeks after nephrectomy. Administered dose in accordance with the SmPC/USPI
 
The estimated number of patients to be randomized is around 90 (with a stratification of intermediate-risk versus high-risk patients). The patients will be randomized in a 2:1 (vaccine treatment arm [i]: control treatment arm [ii]) ratio.
 
Patients randomized to treatment arm (i) are scheduled for 12 study visits during a study period of 78 weeks. Patients randomized to treatment arm (ii) are scheduled for 10 study visits during a study period of 78 weeks. The same visits as for patients randomized to treatment arm (i) apply except for the two (2) vaccination visits. In addition, all patients being exposed to any of the Investigational Medicinal Products (IMPs) will have a safety evaluation done for collection of SAEs up to 30 days after last dose of IMP administered in the study.
 
All patients will be encouraged to contact the clinic in between study visits if they experience adverse events (AEs) or have any concerns. If follow-up of any symptoms is needed between the planned visits, the patient will be scheduled for a visit as soon as possible and applicable assessments will be performed.
 
Post-study survival data (date of death) collection will continue on a yearly basis for a maximum of 5 years after collection of the last patient's 18 months survival data.
	

Name of the Sponsor/Company: Immunicum AB (publ)	Study Code: IM-201
Name of Investigational Medicinal Product: Intuvax	EudraCT No.: 2014-004510-28
Development Phase of the Study: Phase II	Trial under an IND: IND No.: 17081

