11.3 Reporting of Serious Adverse Events

The Investigator is responsible for ensuring that all SAEs are reported to the Sponsor immediately, but in any event no later than 24 hours of any site staff becoming aware of the event. Initial reports should be followed as soon as possible by detailed written reports. The initial and follow-up reports should identify patients by unique code numbers assigned in the study. The patient's names, personal identification numbers, and/or addresses must not be included. The following information is **mandatory** for the initial report:

- Patient study ID
- Study treatment (blinded, if applicable)
- Start date (time, if relevant) of the study treatment
- Brief description of the event (diagnosis)
- Start date (time, if relevant) of the event
- Seriousness criteria
- Causality assessment

For reported deaths, the Investigator should supply the Sponsor and the IRB/IEC (if applicable) with any additional requested information (e.g. autopsy reports and terminal medical reports).

Detailed instructions describing the procedure of reporting SAEs including Suspected Unexpected Serious Adverse Reactions (SUSARs), *Section 11.4*, will be distributed to the site and all involved parties at the Sponsor and [REDACTED] prior to study start.

As a principle, all SAEs must be documented and medically assessed by the Investigator and the outcome described in the AE section of the eCRF.

Follow-up of Post-Study Survival Information

Sites having patients who are still alive after the entire study has ended will be asked to seek survival information in medical records or databases (including public records).

The patient's survival information after the patient's End-of-study Visit will be reported to the safety database only, i.e. will not be included in the clinical database. A survival report form should be used for such reporting.

Post-study survival information will be collected as follows:

- Collection of survival data for the individual patient; at the 18 months post randomization time point
- A complete collection for all applicable patients; at the time of study end (*Section 7.5*)
- A complete collection for all applicable patients; at the last patient's 18 months post randomization time point and thereafter yearly up to 5 years

Updated information on median OS, will be reported to the authorities/IRBs/IECs as addendum(s) to the Clinical Study Report and also as part of the development safety update reports (DSURs).

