NB: Patients alive at the End-of-Study Visit will be followed for survival until date of death can be confirmed or for a maximum of 5 years after collection of the last patient's 18 months survival data, whichever comes first.

Lost to follow-up patients will be handled as censored observations if date of death cannot be found from medical records or databases (including public records).

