- Sunitinib Start Visit (Sun-Start), five (5) to eight (8) weeks after Nephrectomy
- Sunitinib Follow-up Visits (SFU[6W] and SFU[12W]), every 6 weeks for 12 weeks or until locally CT-verified PD whichever occurs first
- Sunitinib Follow-up Visits (SFU[24W], SFU[36W], SFU[48W], and SFU[60W]), every 12 weeks until End-of study or until locally CT-verified PD whichever occurs first
- End-of-Study Visit (End-of-Study)

The above described visits are applicable to all randomized subjects after and including protocol version 4.0. Subjects entering the trial corresponding to protocol versions prior to this, were included following a visit pattern that was different for high and intermediate risk patients. Following this design intermediate risk subjects would only start sunitinib treatment after confirmed PD.

At the two (2) Vaccination Visits, the patients are be administered Intuvax (10 x10⁶ DCs) intratumorally in the viable part of their primary tumor. Vaccine from the same batch (i.e. the same donor) is be used at both occasions. The patient stay at the clinic at least four (4) hours after vaccination. Nephrectomy is done at least 3 days after the second vaccination and maximum 63 days after Screening. Sunitinib treatment is initiated five (5) to eight (8) weeks after nephrectomy, administered dose is in accordance with the SmPC/USPI.

All patients are encouraged to contact the clinic in between study visits if they experience adverse events (AEs) or have any concerns. If follow-up of any symptoms is needed between the planned visits, the patient are scheduled for a visit as soon as possible and applicable assessments are performed.

A diagram of the study design is provided in Figure 1, and a flow chart what all assessments to be conducted per visit are provided in Tables 1 and 2.

Post-study survival data (either patient alive or date of death) will be collected.

[figure not shown]

Figure 1 Overall Study Design

Table 1 Study Flow Chart

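### The OS rule counts deaths found by later record search but censors unlocated patients at an earlier date, with no stated data cut-off; this can bias survival downward

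*SAP*

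**What the plan says.** SAP 6.3.5 gives three rules for OS.

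- Deaths: "patients with a known date of death during the additional collection, the survival time will be calculated as the difference in date of death"; the time runs from randomization, and one day is added.
- Located survivors: "Patients still alive at last contact, either during the trial or at the additional collection, will be censored at last date patient is known alive".
- Unlocated patients: those lost during the trial, and those "alive at end of trial where no follow-up information is available will be censored at last date patient is known alive".

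Protocol 12.1.5 adds: "Lost to follow-up patients will be handled as censored observations if date of death cannot be found from medical records or databases", with public records among the sources searched.

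The same section bases the primary analysis on the data collected at the end of the entire study. If that collection is more than two months from the last patient's 18-month point, a further collection and a follow-up analysis are added. No calendar date is given after which deaths are ignored and at which survivors are censored.

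The documents describe the post-study collection differently. The protocol synopsis says "Post-study survival data (date of death) collection will continue on a yearly basis", and Protocol 7.1 uses the same parenthesis. SAP 4.1 says "Post-study survival data (either patient alive or date of death) will be collected". Under Protocol 11.3, survival information after the patient's End-of-Study Visit is "reported to the safety database only, i.e. will not be included in the clinical database".

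**The concern.** Kaplan-Meier estimation needs observation time that does not depend on vital status. For a patient out of contact, one record search can have two results. A death becomes an event at its date. A search that finds nothing returns the patient to an earlier date, and the time survived since then is lost from the risk set. Deaths in that gap are kept and survival time in it is discarded, so the estimated hazard is too high.

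The gap can matter because study visits stop at progression (Protocol 7.2.1.6 makes that visit the End-of-Study Visit). Much of the survival information therefore comes from the later collections. Protocol 11.3 has sites look in medical records and databases for patients still alive after study end, and it does not ask for a dated confirmation that a patient is alive. At stake are the two primary endpoints and the updated median OS that Protocol 11.3 sends to authorities and ethics committees.

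**Working it through.** The plan has no figure to reproduce: it states no loss rate, event count, design median or expected 18-month rate.

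**1. Treatment of each patient under the rule**

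| Patient | Treatment |
|---|---|
| Dies, death found at any collection | Event at true date |
| Alive, located at a collection | Censored at that later date |
| Not located, no death found | Censored at last date known alive |

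Only the third row creates the asymmetry.

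**2. Assumptions**

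- Exponential OS with median m = 12, 18 or 24.5 months. The last is the phase I high-risk figure in Protocol 5.1, from five patients; the others are assumed.
- Follow-up A uniform over 18 to 51 months. Q2 2015 to Q3 2019 is 17 quarters, and 17 × 3 = 51 months; the uniform shape is assumed.
- A share u of patients leaves contact at a time uniform over 0 to 18 months.
- All their later deaths are found. A share q of their survivors is confirmed alive.

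**3. Formula for the 18-month rate**

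With λ = ln 2 / m, the share wrongly missing from the risk set at month t ≤ 18 is

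d(t) = u(1 − q) · (t/18) · e^(λt) · K, with K = (e^(−18λ) − e^(−51λ)) / (33λ).

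All deaths stay in, so the estimated hazard is λ/(1 − d(t)), and S(18) = exp(−∫₀¹⁸ λ/(1 − d(t)) dt).

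**4. Worked case: m = 18, u = 20%, q = 0**

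- λ = 0.6931/18 = 0.03851; K = (0.5 − 0.1403)/(33 × 0.03851) = 0.283.
- d(0) = 0; d(9) = 0.2 × 0.5 × 1.414 × 0.283 = 0.040; d(18) = 0.2 × 1 × 2 × 0.283 = 0.113.
- Simpson average of 1/(1 − d): (1 + 4 × 1.0417 + 1.1277)/6 = 1.049.
- Cumulative hazard 0.6931 × 1.049 = 0.727; S(18) = 0.483 against a true 0.500, which is −1.7 points.

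**5. Range, by simulation (400,000 patients per scenario, Monte Carlo error about 0.1 point), q = 0**

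| u | m = 12 (true 35.4%) | m = 18 (true 50.0%) | m = 24.5 (true 60.1%) |
|---|---|---|---|
| 5% | −0.3 | −0.4 | −0.4 |
| 10% | −0.6 | −0.9 | −0.7 |
| 20% | −1.3 | −1.7 | −1.9 |
| 30% | −1.9 | −2.6 | −2.9 |

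Entries are points on the 18-month rate. Median OS at u = 20% reads 11.8, 17.2 and 22.6 months. Shorter follow-up enlarges the effect: with 17 to 30 months and m = 18, the rate reads 0.476 at 20% and 0.462 at 30%.

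**6. When it vanishes**

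- All survivors confirmed (q = 1): zero at any u.
- Deaths and survivors each found half the time: zero.
- Half the survivors confirmed at u = 20%: −0.7 to −0.8 points.
- 18-month status obtained for everyone, with gaps only later: zero at 18 months, but a true median of 24.5 reads 23.7 at u = 20%.

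**7. Between arms**

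Equal loss gives about zero. Loss of 30% against 10% gives about 2 points. For scale, with 60 and 30 patients (90 split 2:1) and a rate of 0.5, the standard error of the difference is √(0.25/60 + 0.25/30) = √0.0125 = 0.112, about 11 points.

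**8. Candidate remedies**

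- Censoring everyone out of contact at last contact, whether or not a death is later found, gives about zero bias if loss is non-informative.
- Censoring everyone not found dead at a common cut-off is unbiased only if the death search is complete. If half the deaths are missed (m = 18, u = 20%), the rate reads 0.522 and the median 19.3 instead of 18.0. A cut-off alone is not enough.

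**The case against.** The plan already contains safeguards. Located survivors receive time up to the collection at which they are found. SAP 4.1 collects alive status. Protocol 11.3 seeks survival data for each patient at 18 months, for all applicable patients at study end and at the last patient's 18-month point, and then yearly for up to five years. Protocol 8.5 keeps withdrawn patients in survival collection. A medical-record entry can also move the last-known-alive date forward. If these collections work as written, few patients fall under the early-censoring rule. This stands, and it makes the bias conditional.

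A reader might infer three stronger things.

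- That the rule in itself biases both endpoints downward. It does not: the bias needs survivors who remain unconfirmed after those collections.
- That, because the synopsis and Protocol 7.1 mention only date of death, no survivor has an alive date after exit. Protocol 11.3 speaks of survival data and a survival report form, and SAP 4.1 names alive status, so the parenthesis is a mismatch to reconcile and not the operating procedure.
- That the arm comparison is biased. Nothing in the documents shows that ascertainment differs by arm, although the open-label design makes it possible.

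The trial is also declared exploratory, and at moderate loss the effect is well below the 11-point standard error. That limits the weight of the point but does not remove it. Protocol 12.2 gives adequate estimation of 18-month survival as what the sample size is expected to deliver. SAP 6.3.5 itself foresees patients without follow-up information, and SAP 6.6 adds no sensitivity analysis for them.

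**Conclusion.** The point holds in conditional form. The rule permits one-sided ascertainment and no calendar cut-off is stated. Where deaths are found more completely than survivors are confirmed alive, OS is understated, and so is the 18-month rate to the extent that 18-month status is missing.

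Under the assumptions above, the shift in the 18-month rate is about 0.3 to 1.9 points with 5 to 20% of patients unlocated and about 2 to 3 points at 30%, somewhat more with shorter follow-up. It is zero if all survivors are confirmed. A spurious arm difference of about 2 points needs something like 30% against 10% loss. The loss shares, survival distribution and follow-up range are assumptions, so these are scenarios and not a forecast. The bias is modest, but it is avoidable at little cost and should be closed before database lock.

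**What to change.** In SAP 6.3.5:

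1. Set a data cut-off date for each survival analysis, tied to the corresponding complete collection in Protocol 11.3. Deaths after it are not counted.
2. Censor at the cut-off patients confirmed alive on or after it, or not found dead in a death register with complete coverage to that date.
3. Censor the rest at the last date known alive, and report their number by arm.
4. Add a sensitivity analysis that censors every patient without post-exit contact at last contact, including those whose death was found only by search. It assumes that leaving contact is unrelated to prognosis, which is doubtful when exit follows progression. It should be read beside the main analysis and not replace it.

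Align the protocol synopsis and Section 7.1 with SAP 4.1, so that each collection records either a date of death or a dated alive status. Because these data sit in the safety database, freeze a dated extract for each analysis.

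The cost is SAP and protocol wording, one extra run of the OS and 18-month analyses, and possibly a date field on the survival report form. That form is not in the documents, so the field may already exist. No extra patients or visits are needed.
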